Secondary Endpoint(s): Overall Survival is defined as time from first treatment until death. rPFS will be defined as the time from first treatment day until objective or symptomatic radiologic progression. Progression will be determined by RECIST 1.1 and bone progression is per PCWG2 criteria. PSA progression will be evaluated but will not be considered PD; PSA progression is defined as increase in PSA value of $\geq 25\%$ and an absolute increase of ≥ 2 ng/mL over baseline or nadir. Serum chromogranin A and neuron specific enolase response is defined as obtaining $>50\%$ reduction from baseline. CTC enumeration counts will be classified into favorable (≤ 5) or unfavorable (>5); baseline and post-cycle 2 classification will be compared. In addition, % changes in counts will be assessed. Molecular analysis will be performed on pre-treatment tissue specimens and

plasma DNA.

Study Design:

This is a multi-institutional single-arm, open-label Phase 2 trial evaluating MLN8237 in patients with histologically confirmed or clinically suspected metastatic neuroendocrine prostate cancer (see inclusion criteria for full list of eligibility). All subjects will have a mandatory metastatic tumor biopsy at time of enrollment for research purposes. Subjects will be treated with MLN8237 at 50 mg twice daily for 7 days repeated every 21 days. Individual dose reductions will be made on the basis of the AEs observed. Therapy will continue until disease progression, unacceptable toxicity as a result of MLN8237, or withdrawal of patient consent. Patients will be followed with history, physical, and blood tests at each visit to monitor for toxicity. Response and progression will be evaluated by CT/MRI scan and bone scan after every 3 cycles and determined using RECIST v1.1. PSA and investigational tumor markers (assessed centrally) will be followed every cycle. CTC counts by CellSearch will be performed at baseline, at 4-6 weeks, and upon progression. Patients will be followed for survival endpoints following completion of this study until death.

Main Criteria for Inclusion/Exclusion (summary):

- 1) Metastatic prostate carcinoma and at least one of the following:
 - a) Histologic diagnosis of small cell or neuroendocrine prostate cancer
 - b) Histologic diagnosis of prostate adenocarcinoma plus $\geq 50\%$ immunohistochemical staining for neuroendocrine markers (such as chromogranin, synaptophysin or neuron specific enolase)

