5 CTC counts are encouraged, but are not mandatory and must be performed via CellSearch methodology at the following time points: prior to chemotherapy C1D1 (or within one month prior to treatment), C3D1, and at progression or end of study.

6 Serum chromogranin and neuron specific enolase should be performed locally during screening, then centrally Day 1 of each cycle and at progression

7 Serum carcinoembryonic acid (CEA) level is performed centrally C1D1, after every 3 cycles (at time of scans), and at progression

8 Blood for research will be collected at the following time points: C1D1, C1D8, and at progression or end of study. On C1D1 sample, PBMC and plasma will be isolated separately. At other time points, plasma will be collected.

9 CT/MRI of abdomen/pelvis plus CT of chest; imaging modality should remain constant for the duration of the study (i.e. if baseline scan was MRI, follow up scans should be MRI). See section 7.0 for details

10 Biopsy of metastatic tumor can be performed at any time after informed consent prior to C1D1

11 MLN8237 will be given D1-7 of every cycle

12 Must occur >30 days from last dose of MLN8237; research lab procedures performed as part of progression visit do not need to be repeated

TABLE OF CONTENTS

	Page
PROTOCOL SUMMARY	4
STUDY CALANDER	8
1. BACKGROUND	12
1.1 Neuroendocrine Prostate Cancer	12
1.2 Aurora Kinase A and Prostate Cancer	13
1.3 MLN8237	15
1.4 Correlative Studies Background	23
2. OBJECTIVES	24
2.1 Primary Objectives	24
2.2 Secondary Objectives	25
2.3 Exploratory Objectives	25
3. STUDY DESIGN	25
4. SUBJECTS	26
4.1 Recruitment	26
4.2 Number of Patients	26
4.3 Inclusion Criteria	26
4.4 Exclusion Criteria	27
4.5 Registration Procedure	29
4.6 Duration of Follow-up	29
5. PATIENT EVALUATION	29
5.1 Screening Period	29
5.2 Treatment Period	30
6. CORRELATIVE STUDIES	35
6.1 CTC by Cellsearch	35
6.2 Plasma for research	35
6.3 Serum Tumor Markers	35
6.4 Archival tissue	35
6.5 Metastatic Tumor Biopsy	35
7. RADIOLOGIC EVALUATION	35
8. TREATMENT PLAN	36
8.1 Administration of MLN8237	36
8.2 Dose Modifications/ Delays	36
8.3 Packaging and Labeling	39
8.4 Excluded Medications and Procedures	39
8.5 Permitted Medications and Procedures	39

8.6	Precautions and Restrictions	40
8.7	Management of Clinical Events	41
8.8	Treatment Compliance	42
8.9	Duration of Treatment	42
8.10	Termination of Treatment and/or Study Participation	43
9.	STUDY DRUG ADMINISTRATION	43
9.1	Description of MLN8237	43
9.2	Preparation and Dispensation	44

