Blood: Shedding of circulating tumor cells (CTCs) into the circulation is common in advanced prostate cancer. The CellSearch (Veridex LLC, Warren, NJ) automated enrichment system capture device is an FDA-cleared technology for detecting and quantifying EpCAM expressing tumor cells in the blood and has prognostic value. A CTC count ≥ 5 per 7.5 mL of blood is considered unfavorable and <5 is favorable; furthermore, changes in CTC count on therapy is reflective of prognosis and therefore serial CTC counts are being validated prospectively as alternative biomarker of tumor response for patients with advanced prostate cancer. CTC counts by CellSearch are encouraged as part of this study, but are not mandatory. Blood will also be obtained on day 1 of each cycle and evaluated for neuroendocrine markers (serum chromogranin and NSE), lactate dehydrogenase (LDH), and prostate specific antigen (PSA).

In addition, blood for research (plasma and PBMC's) will be collected for research on C1D1, C1D8, and at progression or end of study. Plasma DNA will be evaluated for Aurora A and N-myc amplification and correlated with response to therapy and tumor tissue status. In addition, we will evaluate for concordance between plasma DNA molecular alterations and matched primary prostate cancer tissue and metastatic samples. We will correlate these results with clinical response to MLN8237.

Archival Tissue: Formalin fixed paraffin embedded (FFPE) archival prostate tumor tissue will be obtained from all patients (prostatectomy specimens or prostate biopsies) and evaluated for AR, ERG, aurora kinase A, N-myc protein expression, copy number changes, and/or translocation (in case of ERG). We hypothesize that high-risk primary prostate tumors harbor genetic alterations that predispose to clinical progression and the development of NEPC. Using the MiSeq technology (Illumina), we will perform targeted exome sequencing of matched primary tumors from 30 patients that later developed

metastatic NEPC. We will take a focused approach to examine non-synonymous recurrent mutations in FFPE tissue. Through molecular classification and correlation with clinical features and between matched primary tumors and metastases, we will gain insight into genetic alterations that arise early and predispose to the development of NEPC and will correlate with outcomes and clinical response to MLN8237.

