2.2 Secondary objectives

- To determine the overall survival with MLN8237
- To evaluate the objective response rate
- To determine the progression free survival with MLN8237
- To determine the PSA response rate with MLN8237
- To determine baseline and changes in circulating tumor cell count in response to therapy and at disease progression
- To determine serum neuroendocrine marker response with MLN8237

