- Withdrawal of patient consent
- Noncompliance with protocol-specified procedures which in the opinion of the investigator will expose subjects to undue risk or will significantly effect interpretation of study results

12. Statistical Considerations.

12.1. Sample Size Justification:

The primary endpoint is the proportion of patients who are free from radiographic progression at 6 months following treatment with MLN8237. Based on the phase II trial by Meulenbeld et al (BJUI 2012), the proposed null hypothesis (H_0) is that $\leq 15\%$ of patients will be radiographic progression-free at 6 months and the alternative hypothesis (H_a) is that $\geq 30\%$ of patients will be radiographic progression-free at 6 months.

Sample size recommendations for the phase II design are determined according to Ahern's exact single-stage phase II design (A'Hern RP, 2001). We project a 6-month radiographic progression-free proportion of 15%, below which the response will be unacceptable, and a 6-month radiographic progression-free proportion of 30%, above which the regimen will be considered worthy of further exploration. The null hypothesis that the 6-month radiographic progression-free proportion is less than or equal to 15% will be tested against the alternative hypothesis that the 6-month radiographic progression-free proportion is greater than or equal to 30%.

The sample size computations were performed assuming a 5% level of significance and 80% power. A total of 48 patients will be required to enroll in the study. The treatment will be declared effective and worthy of further testing if 12 or more patients are free from radiographic progression at 6 months among the 48 patients entered into the study. This exact single-stage design yields a ≥ 0.80 probability of a positive result if the true percentage of patients who are free from radiographic progression at 6 months is $\geq 30\%$. It yields a ≥ 0.95 probability of a negative result if the true percentage of patients who are free from radiographic progression at 6 months is $\leq 15\%$. Assuming 10-20% of patients will be unevaluable/ineligible, we anticipate that a total 60 patients will be enrolled in the study.

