12.3.2 Serum marker response (PSA, chromogranin, neuron specific enolase)

Serum PSA, chromogranin, and neuron specific enolase (NSE) responses are determined by comparing the nadir level after therapy to the baseline, pre-treatment level determined just prior to initiating therapy. Declines of $\geq 30\%$ and 50% , confirmed by a value ≥ 2 weeks later, will be reported. Serum marker progression will be defined as a rise of $> 25\%$ above either the pretreatment level or the nadir level (whichever is lowest). PSA must increase by > 2 ng/ml to be considered progression. Confirmation requires a second consecutive rising PSA, chromogranin, or NSE at least 2 weeks apart. Marker stabilization is referred to as any set of values that do not meet the criteria for response or PSA progression.

12.3.3 CTC count response (CellSearch). Baseline CTC counts of < 5 when measured by CellSearch methodology have been associated with better prognosis (overall survival).[34, 35] In addition, changes in CTC counts after initial therapy have been demonstrated to be predictive.[36] We will explore the prognostic and predictive significance of 4 groups as has been described:

Baseline < 5 , follow up < 5
Baseline ≥ 5 , follow up < 5
Baseline < 5 , follow up ≥ 5
Baseline ≥ 5 , follow up ≥ 5

In addition, we will report individual subject's CTC count change from baseline.

13.0 Data Collection The data collection plan for this study is to utilize a study-specific (WCMC CTSC-supported) REDCap database to capture all treatment, toxicity, and efficacy data for all enrolled patients.

13.1 Confidentiality In order to protect confidentiality of the data, patient full names will be removed and data coded with patient initials and study subject numbers. All primary data will be kept in locked file cabinets or password-protected computers and available only to the investigators and appropriate regulatory personnel (e.g., IRB, FDA, etc.).

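### The synopsis adds percentage change in CTC count, a scale with no value at a baseline of 0 and biased at low counts; absolute and log(count+1) change would serve better

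*Protocol*

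**What the plan says.** The synopsis lists CTC response among the secondary objectives. Under Secondary Endpoint(s) it gives two summaries. The first is categorical: "CTC enumeration counts will be classified into favorable (≤ 5) or unfavorable (>5); baseline and post-cycle 2 classification will be compared". The second is the supplementary line at issue: "In addition, % changes in counts will be assessed".

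Section 2.2 words the objective in terms of counts, with no percentage: "To determine baseline and changes in circulating tumor cell count in response to therapy and at disease progression".

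Section 12.3.3 cross-classifies baseline and follow-up at a cut of 5: "We will explore the prognostic and predictive significance of 4 groups as has been described". Two of those four groups have a baseline below 5. It then adds: "In addition, we will report individual subject's CTC count change from baseline". It does not say whether that change is a difference or a percentage.

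Section 1.4 gives the unit and the cut-off: "A CTC count ≥ 5 per 7.5 mL of blood is considered unfavorable and <5 is favorable".

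Sections 4.3 and 4.4 set no minimum CTC count, and the test is optional. Footnote 5 of the study calendar says: "CTC counts are encouraged, but are not mandatory".

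**The concern.** A CTC result is a whole number of cells in a fixed blood volume, and the protocol plans for baselines of 0 to 4. A percentage of such a baseline behaves badly in three ways.

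- At 0 it does not exist.
- At 1 to 4, a single cell moves it by 100 to 25 percentage points.
- It cannot fall below -100% but has no upper limit, so its average is off zero even when nothing has changed.

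As an illustration, a man who goes from 1 cell to 3 scores +200% and stays favorable. A man who goes from 200 to 100 scores -50% and stays unfavorable. The trial has a single arm, so there is no control group to show how much apparent change is counting error.

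At stake is the readability of one descriptive line for a named secondary endpoint. In addition, the synopsis says percentage while sections 2.2 and 12.3.3 speak of change in count, so two analysts could report different quantities under the same endpoint.

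**Working it through.** **No plan figure to reproduce.** The protocol states no number for the CTC endpoint.

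**Inputs from the protocol.** Integer counts per 7.5 mL (section 1.4); no minimum count at entry (sections 4.3 and 4.4); cut-off at 5 (synopsis, sections 1.4 and 12.3.3).

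**Assumption, not in the protocol.** Baseline X and follow-up Y are independent Poisson counts with the same mean m, so there is no true change. A range of m is shown because the protocol gives no CTC distribution.

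**Formulas.**
- Chance that the percentage is undefined: P(X = 0) = exp(-m).
- Expected percentage change where defined: E[(Y - X)/X | X > 0] = m × E[1/X | X > 0] - 1.
- Approximate standard deviation of the percentage change: √(2/m).
- Chance of an apparent change, or an apparent fall, of 50% or more: exact sums over the two Poisson distributions, given X > 0. The 50% level only illustrates the noise; the protocol sets no such threshold for CTCs.

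**Numbers put in.** At m = 2, exp(-2) = 0.135. At m = 5, E[1/X | X > 0] = 0.2578, so the expected change is 5 × 0.2578 - 1 = +0.289. At m = 10, it is 10 × 0.1130 - 1 = +0.130. At m = 5, √(2/5) = 0.63.

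| Mean m | Baseline 0 | Mean % change | Change of 50% or more | Fall of 50% or more |
|---|---|---|---|---|
| 1 | 36.8% | -23% | 70.5% | 52.7% |
| 2 | 13.5% | +15% | 66.9% | 37.0% |
| 3 | 5.0% | +30% | 60.3% | 28.1% |
| 5 | 0.7% | +29% | 47.5% | 18.6% |
| 10 | 0.0% | +13% | 28.7% | 8.4% |
| 20 | 0.0% | +5.6% | 13.3% | 2.2% |
| 50 | 0.0% | +2.1% | 2.5% | 0.1% |

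The bias is upward at every mean shown from 2 on and fades as the count rises. At a mean of 1 it is negative, because leaving out the zeros keeps only men whose baseline happened to be high. The noise also fades gradually, with no natural limit at 10 or elsewhere.

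**Alternative scale.** Under the same model, X and Y have the same distribution, so Y - X and log(Y+1) - log(X+1) both have expectation exactly 0 at every m. Both are defined at X = 0.

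**Restricting percentages to high baselines.** At m = 5 with no true change:

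| Men included | Mean % change | Fall of 50% or more |
|---|---|---|
| baseline above 0 | +29% | 18.6% |
| baseline ≥5 | -20% | 27% |
| baseline >5 | -29% | 34% |

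Selecting on a high, noisy baseline turns the bias into an apparent benefit. This is regression to the mean.

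**Cut-off.** The synopsis classes a count of exactly 5 as favorable (≤5). Section 1.4 calls it unfavorable (≥5), and section 12.3.3 groups it with the higher counts (≥5).

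**The case against.** The strongest reply is that little hangs on this line. The main CTC summaries are the class comparison and the four groups. Percentage change is an addition with no threshold, test or decision attached, in a test that is optional. Section 12.3.3 already reports each man's change in count, which is defined at 0, and nothing prevents both from being reported. Handling of zeros and choice of transformation are commonly left to the statistical analysis plan. The number of men affected cannot be derived.

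Most of that stands, and it limits the size of the point. A reader might infer that the CTC response analysis as a whole loses men with a baseline of 0. It does not: 0 is favorable under either cut-off and falls in one of the four groups. A reader might also infer that the protocol counts 50% falls, or averages percentages, for CTCs. It states neither; its 50% levels belong to the serum markers (PSA, chromogranin A and neuron specific enolase). Nor does it say that men with a baseline of 0 will be excluded; it is silent on them.

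The reply does not rescue the metric. The protocol names percentage change as a summary of a secondary endpoint, so this is a choice it makes and not a detail it omits.

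**Conclusion.** The point holds as a minor improvement. Percentage change in CTC count is undefined at a baseline of 0, which the entry criteria allow. At low counts its average departs from zero with no true change: about +29% at a mean of 5 and +13% at a mean of 10, falling to +2.1% at 50. These figures rest on Poisson counting error with independent visits and a common mean; they illustrate the scale and do not predict this trial's data. The class comparison, the four groups and the primary decision rule are untouched. Separately, the passages contradict each other on a count of exactly 5, and that needs no assumption.

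**What to change.** In the synopsis, replace the percentage line with absolute change and change in log(count+1) for all men with paired counts, and use the same wording in section 12.3.3. If percentages are wanted, list them for individual men beside the raw counts. Do not average them, and do not summarise them in a subgroup chosen for a high baseline.

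In the same edit, adopt one cut-off for the analysis in the synopsis, section 1.4 and section 12.3.3, so that a count of exactly 5 has one class.

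The cost is a few sentences and no new data. The small downside is that clinical readers know the log scale less well than a percentage; the absolute change and raw counts shown with it help.

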1.1 Neuroendocrine prostate cancer

Prostate cancer is a leading cause of cancer mortality in men worldwide (Siegel et al, *Cancer Statistics*, 2012). Those that die from prostate cancer die from metastatic castration resistant prostate cancer (CRPC), tumors that progress after surgical or medical castration. We know now that many CRPC tumors remain dependent on androgen receptor (AR) signaling due to AR gene amplification, intra-tumoral androgen production, constitutive activation of AR, or other proposed mechanisms (Knudsen et al, *Clin Cancer Res* 2009). This knowledge has led to the clinical development of novel and highly potent drugs that block AR signaling, through inhibition of hormone production (e.g. abiraterone acetate) or AR receptor binding (e.g. enzalutamide).

An often under-recognized late manifestation of prostate cancer is the development of neuroendocrine prostate cancer (NEPC), which is considered a hormone refractory (AR negative) subtype of prostate cancer ([name] et al, *Textbook of Uncommon Cancer*, 4th Ed, 2012). These tumors do not secrete prostate specific antigen (PSA), and should be suspected in a patient with progressive disease (especially visceral or lytic bone metastases) in the setting of a low or modestly elevated PSA. Based on autopsy series and other studies, NEPC may represent approximately 25% of late stage prostate cancer (Aparicio et al, *Cancer Discovery* 2011). Transformation from prostate adenocarcinoma to NEPC is believed to be promoted by androgen deprivation therapy (Hirano et al, *Eur Urol* 2004), and many are concerned that with the introduction of novel potent AR-targeted drugs into the clinic for CRPC the incidence of NEPC will escalate ([name] et al, *J Clin Oncol* 2012).

Histologically NEPC can appear like small cell carcinoma of other primary sites, does not express AR or secrete PSA (Palmgren et al, *Semin Oncol* 2007), and can sometimes be misdiagnosed.

Immunohistochemical staining of tumors are often positive for neuroendocrine markers chromogranin A, synaptophysin, or neuron specific enolase (NSE), and elevated serum levels of chromogranin A, NSE, and carcinoembryonic antigen can support the diagnosis. Gene fusions involving the *ERG* gene (most commonly rearranged with the *TMPRSS2* gene), are prostate-specific molecular alterations and present in approximately 50% of all prostate cancers (Tomlins et al, *Science* 2005), with a similar frequency in prostate adenocarcinoma and NEPC (Lotan et al, *Mod Pathol* 2011, Scheble et al,

Histopathology 2010). This suggests that the molecular events associated with NEPC pathogenesis differs from small cell carcinomas of other primary sites, and likely has same cell of origin as prostate adenocarcinoma.

There is little prospective data regarding treatment of patients with NEPC. Platinum based chemotherapy regimens similar to those used to treat small cell lung carcinomas are often used (Papandreou et al, *JCO* 2002). However, relapses are common and most patients with NEPC survive less than one year.

1.2 Aurora kinase A and Neuroendocrine prostate cancer

In attempts to identify biomarkers and develop new treatment strategies for patients with NEPC, we performed massively parallel, paired end RNA- sequencing (RNA-Seq) and genomic analysis using oligonucleotide arrays of prostate tumors and compared the expression profile of NEPC with prostate adenocarcinoma (PCA) and benign prostate ([name] et al, *Cancer Discovery* 2011).

There were significant molecular differences between NEPC and PCA, despite likely clonal origin (based on concordance of molecular alterations between primaries and metastases and between NEPC and PCA foci of mixed tumors). Aurora kinase A (AURKA) was significantly overexpressed and amplified in NEPC vs PCA ($P<0.001$), and this was independent of tumor proliferation (Ki67 expression). AURKA encodes Aurora kinase A, a serine/threonine kinase involved in mitotic spindle formation, centrosome separation, and G2-M transition during the cell cycle (Marumoto et al, *Genes to Cells* 2002). Beyond its role mitosis, Aurora- kinase A also displays oncogenic properties (can transform rat fibroblasts in vitro and produce tumors in athymic mice), though its full range of function is not well elucidated (Katayama et al, *Cancer and Metastasis Reviews* 2003). In neuroblastoma, AURKA is found to stabilize N-myc, an oncogene frequently amplified in neuroblastoma and associated with poor prognosis (Otto et al, *Cancer Cell* 2009). N-myc is not normally present in prostate, but we also found its gene (MYCN) to be overexpressed and amplified in NEPC compared to PCA ($P<0.001$). We validated these findings by screening prostate samples from a large cohort of patients using immunohistochemistry (IHC) and fluorescent in situ hybridization (FISH), and discovered gene amplification of AURKA and MYCN in 40% of NEPC, 5% of PCA, and none of the benign prostate tissue. Furthermore, concurrent AURKA and MYCN amplification is seen in 75% of primary prostate

tumors from patients that late develop NEPC and with a high concordance between primary tumor and metastases (suggesting that these lesions are early events and may be prognostic).

When we introduced AURKA or MYCN into benign prostate epithelial cells (RWPE-1) and prostate adenocarcinoma cells (LNCaP), MYCN induced AURKA expression and kinase activity by stabilizing Aurora A protein, and AURKA induced MYCN. Furthermore, either AURKA or MYCN could induce expression of the neuroendocrine markers, synaptophysin or neuron-specific enolase, not normally expressed in RWPE-1 or LNCaP cells. This data suggests that AURKA and MYCN are involved in prostate neuroendocrine differentiation.

LNCaP transfected with N-myc were phenotypically similar to NEPC, with downregulation of AR and androgen regulated genes (NKX3-1, TMPRSS2), and chromatin immunoprecipitation revealed that N-myc directly binds promoters of NSE, SYP, and AR to regulate their expression and modulate the neuroendocrine phenotype. N-myc amplified neuroblastoma cells (IMR-32) also demonstrated N-myc binding to NSE and SYP but not AR, suggesting that N-myc binding of AR promoter is prostate specific.

Based on these data, we hypothesized that aurora kinase inhibition would demonstrate preferential anti-tumor effect in NEPC compared to PCA. In support of this, we observed enhanced *in vitro* and *in vivo* sensitivity of NEPC cells and xenografts treated with the aurora kinase inhibitor PHA-739358 (Danusertib, Nerviano), compared to PCA models and benign prostate cells, with > 50% tumor shrinkage in NEPC xenografts and minimal to no effect in PCA. Notably, neuroendocrine marker expression (synaptophysin) was completely suppressed in the treated NEPC xenografts, again supporting a role of Aurora kinase in modulating the neuroendocrine phenotype. Knockdown of AURKA with siRNA in NEPC cells (NCI-H660) also resulted in significant cell death (50-60% decreased viability) and suppression of neuroendocrine marker expression.

MLN8237 is an orally administered Aurora kinase A inhibitor that has demonstrated broad antitumor activity in vitro and in vivo, and the RP2D as monotherapy in adults with refractory solid tumors was 50 mg BID for 7 days in 21-day cycles (Dees *et al.*, ASCO 2010).

We hypothesize that NEPC patients (and a subset of PCA) will preferentially benefit from MLN8237, based on:

- 1) Aurora-A and its inducer, N-myc, can drive the NEPC phenotype and are overexpressed and amplified in NEPC and a small subset of PCA;
- 2) Knockdown of Aurora kinase A (AURKA) resulted in decreased viability and suppression of neuroendocrine marker expression in NCI-H660 (NEPC) cells;
- 3) Aurora kinase inhibitor therapy demonstrate significant and preferential anti-tumor effect in NEPC xenografts and results in complete reversal of neuroendocrine marker expression.

